9.7.3 Adverse Events

All AEs will be coded to preferred term and system organ class using MedDRA 17.0 or higher. An AE that started or increased in severity during the treatment-emergent period (refer to [Section 7.1](#)) will be considered a TEAEs. Severity of TEAEs will be graded according to the National Cancer Institute Cancer Therapy and Evaluation Program Common Terminology Criteria for Adverse Events (CTCAE). A study drug-related TEAE is defined as any TEAE with at least a possible relationship to the study drug as assessed by the investigator or that is missing the assessment of causal relationship whose relationship to the study drug could not be ruled out.

Patients with multiple occurrences of events for a given preferred term, system organ class, or overall will only be counted once at the worst severity and strongest relationship to study drug for each preferred term, system organ class, and overall, respectively. AEs that are continuous but change in grade, relationship, or seriousness will be counted as 1 event. TEAEs of unknown severity will be categorized separately. A TEAE of unknown relationship will be considered to be probably related to study drug.

Tabular summaries including numbers and percentages of the following adverse events will be provided:

- Overview of TEAEs;
- TEAEs by SOC and PT;
- TEAEs by SOC, PT, and severity;
- TEAEs by SOC, PT, and relationship to study drug;
- TEAEs leading to study drug discontinuation;
- Serious TEAEs by SOC, PT, and severity;
- Serious TEAEs by SOC, PT, and relationship to study drug;
- Immune Related TEAEs by SOC and PT;
- TEAEs leading to death by SOC and PT.

Listings will be provided for all TEAEs.

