It is at the discretion of the investigator whether to continue a patient on study treatment until repeat imaging is obtained. If repeat imaging confirms PD, patients will be discontinued from the study.

Two dosing delays of pembrolizumab due to toxicity will be permitted. In the event of a third occurrence of a toxicity which would require dosing delay, pembrolizumab will be discontinued permanently.

If a subject resumes pembrolizumab treatment after a dose interruption, the interval between pembrolizumab dosing should not be less than 3 weeks (\pm 3 days) with subsequent return of pembrolizumab dosing to per protocol schedule of events.

Dosing interruptions for SD-101 or pembrolizumab are permitted in the case of medical/surgical events. For Phase 2, dosing interruptions for logistical reasons not related to study therapy (eg, elective surgery, unrelated medical events, patient vacation, and/or holidays) are permitted. Patients should be placed back on trial treatment within 3 weeks of the scheduled interruption, unless otherwise discussed with the Dynavax Medical Monitor.

The reason for any interruption in treatment should be documented in the patient's study record.

7.7 Dose Modification and Toxicity Management for Immune-Related Adverse Events Associated With Pembrolizumab

Adverse events associated with pembrolizumab exposure may represent an immunologic etiology. These immune-related AEs (irAEs) may occur shortly after the first dose or several months after the last dose of pembrolizumab treatment and may affect more than one body system simultaneously. Therefore, early recognition and initiation of treatment is critical to reduce complications. Based on existing clinical study data, most irAEs were reversible and could be managed with interruptions of pembrolizumab, administration of corticosteroids and/or other supportive care. For suspected irAEs, ensure adequate evaluation to confirm etiology or exclude other causes. Additional procedures or tests such as bronchoscopy, endoscopy, or skin biopsy may be included as part of the evaluation. Based on the severity of irAEs, withhold or permanently discontinue pembrolizumab and administer corticosteroids. Dose modification and toxicity management guidelines for irAEs associated with pembrolizumab are provided in [Table 7-1](#).

Table 7-1: Dose Modification and Toxicity Management Guidelines for Immune-related Adverse Events Associated with Pembrolizumab

General instructions:

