9.0 MANAGEMENT OF TRIAL TREATMENT TOXICITIES

NOTE: As of Amendment 9, Phase 1 of the trial is complete. Phase 2 of the trial has been modified to continue dosing per protocol. The collection of safety endpoints has been simplified. Decisions on treatment discontinuation should be made per Investigator based on local standard of care. This section has been updated accordingly.

Safety will be evaluated through the careful monitoring of all clinical and laboratory AEs. Safety assessments may include vital signs, weight, physical examinations, ECOG PS, electrocardiograms (ECGs) and laboratory safety tests (eg, complete blood count [CBC], serum chemistry, PTT or aPTT, urinalysis, thyroid function). See Section 10.3.6 for additional details of laboratory testing. Special attention will be given to immune-related adverse effects (eg, gut, skin, liver, endocrine organs).

All AEs will be graded and recorded throughout the trial according to National Cancer Institute (NCI) CTCAE, Version 4.03. The severity of the local post-injection reactions, including those that become AEs because they persist more than 7 days, will be graded using the Toxicity Grading Scale for Healthy Adult and Adolescent Volunteers Enrolled in Preventive Vaccine Clinical Trials ([Appendix 5](#)). Characterization of toxicities will include time to onset, severity, and duration. Safety endpoints will include all types of drug-related AEs and SAEs regardless of causality.

Phase 1 will be reviewed by a Safety Review Team comprised of the Dynavax Medical Monitor, Phase 1 coordinating investigator, and other key safety Dynavax personnel as described in the Cohort Safety Review Plan. Before Dose Escalation at each dose level of SD-101 and at any other time during Phase 1 or Phase 2 that warrants additional review due to emerging safety data, the investigators will discuss and review the safety data with the Dynavax Medical Monitor.

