9.1 Dose-limiting Toxicity Definitions and Stopping Rules (*COMPLETE*)

Standard safety monitoring will be employed for DLT assessment and dose-escalation decisions. All AEs will be considered in DLT assessment unless an event is clearly unrelated to trial treatment.

Before Dose Escalation at each dose level of SD-101 and at any other time that safety data warrant review, the investigators will participate in a teleconference with the Dynavax Medical Monitor to review all safety data. Additionally, at all times during the course of the study, an increased frequency of Grade 3 immune-related AEs to 2 times that which would be anticipated with pembrolizumab alone will require a halt in accrual and a review of all safety data by the sponsor and investigators.

All AEs, including DLTs, are to be reported according to instructions in the Study Reference Manual and graded using NCI CTCAE, Version 4.03 ([National Cancer Institute 2010](#)). If a patient experiences a DLT, he or she will be treated according to clinical practice and will be monitored for resolution of the toxicity.

The safety profiles of SD-101 (see Investigator's Brochure) and pembrolizumab ([Merck & Co. 2015](#)) as monotherapies have been previously described. The safety profile of the combination of the drugs is unknown. Toxicity of the combination of SD-101 and pembrolizumab may likely manifest as there might be an increase in the frequency, severity, or duration of known toxicity such as flu-like illness due to SD-101 or immune-related AEs due to pembrolizumab. The outcome of a DLT considered related to SD-101 will be discontinuation of SD-101. Toxicity due to pembrolizumab will lead to dose interruption and/or discontinuation as described in Section 7.6 and be managed according to Section 7.7. DLTs considered related to the combination of the

2 drugs will be reviewed and assessed in a teleconference with the Dynavax Medical Monitor and the investigators.

For Dose Escalation purposes, a DLT will be defined as any of the following AEs occurring from the time of the first injection (Day 1) through Study Day 29 of any of the following:

Non-hematologic adverse event

- Grade ≥ 3 non-hematologic AE related to SD-101 (eg, post-injection reaction or influenza-like illness) that does not resolve to Grade ≤ 1 with standard treatment by the time of the next treatment, with the exclusion of fatigue

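### SAP 9.7.3 summarizes immune-related adverse events without grade, so no planned table gives the proportion of patients with a severe immune-related event

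*SAP*

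**What the plan says.** SAP 9.7.3 lists nine adverse event summaries. Two are crossed with grade: "TEAEs by SOC, PT, and severity" and "Serious TEAEs by SOC, PT, and severity". Immune-related events appear once, as "Immune Related TEAEs by SOC and PT". The section ends with "Listings will be provided for all TEAEs", and SAP 9.9 plans nothing further. The SAP does not say how an event is classed as immune-related.

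The protocol gives grade and timing more weight. Section 9.0 asks for particular attention to immune-related effects and, in its next paragraph, states: "Characterization of toxicities will include time to onset, severity, and duration". Section 9.1 requires accrual to stop and all safety data to be reviewed if there is "an increased frequency of Grade 3 immune-related AEs to 2 times that which would be anticipated with pembrolizumab alone"; this applies throughout the study. Section 7.7 warns that immune-related events can start early or "several months after the last dose of pembrolizumab treatment and may affect more than one body system simultaneously".

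**The concern.** Whether adding SD-101 makes pembrolizumab's immune toxicity more frequent or more severe is one of the safety questions that Protocol 9.1 raises about the combination. A count by preferred term with no grade puts a Grade 1 thyroid finding and a Grade 4 colitis on the same footing. A reader of the final report would want one figure per group: how many patients had a severe immune-related event. No summary listed in the SAP supplies it. By contrast, SAP 9.7.2 tabulates injection-site reactions and injection-related general symptoms by maximum severity.

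**Working it through.** There is no design figure to reproduce, because the point is about a missing summary. The check asks whether the other planned outputs supply it.

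**1. The outputs side by side**

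| Output (SAP 9.7.3, 7.3) | Restricted to immune-related? | Grade? | Timing? |
|---|---|---|---|
| All TEAEs by severity | No | Yes | No |
| Serious TEAEs by severity | No | Yes | No |
| Immune-related TEAEs | Yes | No | No |
| Listing of all TEAEs | No flag named | Not named | Original dates; AE duration is a derived item |

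**2. Can the tables be combined?** For one preferred term in one column, take one event per patient. Let t be the patients with the term, m those for whom it is immune-related, and s those with maximum grade 3 or higher. The severity table gives t and s; the immune-related table gives m. The number with a severe immune-related event of that term lies between max(0, m + s − t) and min(m, s).

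- If every case is immune-related (m = t), both ends equal s and the number is known.
- If m < t, as can happen for diarrhea or raised ALT, the range can open and the number need not be known.
- Across terms, the patient count lies between the largest lower end and the sum of the upper ends, because one patient can appear under several terms. Protocol 7.7 expects such multi-system cases.

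**3. Can the overall row of the severity table stand in?** No. Protocol 2.6 gives Grade ≥3 treatment-related events in 59.1% of patients (13/22 = 59.1%), the most common being myalgia and injection-site pain. Immune-related events of any grade occurred in 2/22 = 9.1% (exact 95% CI 1.1% to 29.2%). The overall row mostly reflects other toxicity.

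**4. What the Phase 1 text leaves open.** Protocol 2.6 describes a Grade 2 pneumonitis on Day 23 and a hypophysitis 85 days after last treatment, with no grade for the latter. Assuming one immune-related event per patient, the Grade ≥3 immune-related rate is one of:

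- 0/22 = 0% (exact 95% CI 0% to 15.4%)
- 1/22 = 4.5% (exact 95% CI 0.1% to 22.8%)

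**5. Extent.** SAP 9.11 sets out 4 tumor-by-experience groups × 2 doses = 8 Phase 2 columns, plus 4 Phase 1 dose groups.

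**6. How few events matter.** The documents give no pembrolizumab-alone rate p0, so the values below are assumptions. The sizes 25 and 50 are planned expansion cohort sizes, not the sizes of the pooled columns. The threshold r is the smallest whole number ≥ 2 × p0 × n; for example, 2 × 0.05 × 25 = 2.5, so r = 3. Probabilities are binomial tails.

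| n | Assumed p0 | r | P(X ≥ r), true rate p0 | P(X ≥ r), true rate 2 × p0 |
|---|---|---|---|---|
| 25 | 3% | 2 | 0.172 | 0.447 |
| 25 | 5% | 3 | 0.127 | 0.463 |
| 25 | 10% | 5 | 0.098 | 0.579 |
| 50 | 3% | 3 | 0.189 | 0.584 |
| 50 | 5% | 5 | 0.104 | 0.569 |
| 50 | 10% | 10 | 0.025 | 0.556 |

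In a group of 25, a doubling corresponds to 2 to 5 patients. A table without grade does not isolate them, and any proportion needs an interval beside it.

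**7. Late events.** Protocol 10.3.9 collects AEs to 28 days after the last dose; SAEs run longer (10.3.10). SAP 7.1 counts AEs as treatment-emergent to 90 days. Since 28 < 85 < 90, an event timed like the hypophysitis falls inside the SAP window but, if non-serious, outside the protocol's collection period.

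**The case against.** The strongest reply is that this is a modest reporting gap. Several points in it stand.

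- **The halt rule.** A reader might infer that a stopping decision is at risk. The documents do not support that. The rule governed accrual through ongoing safety review, its section is marked complete, and enrollment is closed in all cohorts at Amendment 9. A graded table alone also could not show whether the criterion was met, because no reference rate is given.
- **The listings.** A reader might infer that grade and timing vanish from the report. That goes too far: all TEAEs are listed, and SAP 7.3 says listings show original dates and treats AE duration as a derived item. A listing is not a summary, however, and no immune-related flag is named.
- **The two Phase 1 events.** They would not merge. Pneumonitis and hypophysitis are separate preferred terms, and the general severity table would show their grades.
- **The protocol's wording.** The sentence on onset, severity and duration is general and sits in a toxicity-management section; the special attention to immune-related effects is in the paragraph before it. Together they show the protocol's emphasis, not a promise of a specific table. Nor does Protocol 9.1 rank immune toxicity first: it names flu-like illness beside it.
- **No label as not implemented.** This proves little, since SAP 1.0 uses that label for objectives.
- **The unseen specifications.** Table and listing specifications are in a separate document, and the content of the TEAE overview is not stated. Either might hold more.

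None of these supplies a patient-level rate of severe immune-related events.

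**Conclusion.** The point holds as a gap in final reporting that is cheap to close. By the summaries the SAP lists, the proportion of patients with a Grade 3 or higher immune-related TEAE is missing from all eight Phase 2 columns and the Phase 1 dose groups. It cannot in general be recovered from the other tables, although it can be for a term whose cases are all immune-related. The conclusion assumes that the separate table specifications do not already add grade to the immune-related table. It does not depend on the assumed reference rates, which only illustrate how few patients are involved.

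**What to change.** In SAP 9.7.3, replace the immune-related line with: *Immune-related TEAEs by SOC, PT and maximum CTCAE grade, with the number and percentage of patients with any Grade 3 and any Grade ≥3 immune-related TEAE (exact 95% CI), by dose or analysis group.* Both cut-offs are needed because Protocol 9.1 refers to Grade 3 only.

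Then:

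- State how an event is classed as immune-related and who decides. The categories in Protocol Table 7-1 can group the terms but do not settle whether a given case of diarrhea or raised ALT qualifies. SAP 9.7.2 already names the Medical Monitor as deciding for injection-related symptoms.
- Flag immune-related events in the TEAE listing, with grade, onset day from first and last dose, and duration. Name the drug from which onset is counted: Cohorts 1 and 3 start pembrolizumab on Day 1 and SD-101 on Day 22, 21 days apart.
- Add a note that non-serious AEs are collected only to 28 days after the last dose, so late non-serious onsets are incompletely captured.
- If the report comments on the two-times criterion, it must state the reference rate used and its source.

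The cost is one revised table, one listing flag and a short definition. Maximum grade is recorded under Protocol 11.4.1, and SAP 7.3 already uses AE dates. Classing events as immune-related may need a medical review. No clinical rule or data collection changes.

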9.7.4 Laboratory Assessments

Laboratory test results for neutrophils, lymphocytes, and platelets and their change from baseline will be summarized by tumor type and scheduled visit.

Laboratory data listings will not be produced as clinically significant abnormal laboratory findings are included in AE data.

Anti-dsDNA antibodies (not implemented) and anti-SD-101 antibodies results will be provided as part of the Annex 1 analysis.

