As described in the table below, melanoma Dose Expansion cohorts in Phase 2 will be treated with 8.0 mg or 2.0 mg of SD-101 in combination with 200 mg pembrolizumab every 3 weeks across 3 cohorts. Phase 2 Expansion Cohort 1 will enroll approximately 60 and Cohort 5 will enroll approximately 25 anti-PD-1/L1 naïve patients with melanoma. Cohort 2 will enroll approximately 25 and Cohort 8 will enroll approximately 50 melanoma patients who have disease progression on anti-PD-1/L1 therapy. In melanoma Dose Expansion Cohort 1, SD-101 dosing starts on Day 22 at the second dose of pembrolizumab; whereas, in Cohorts 2, 5, and 8, SD-101 and

pembrolizumab dosing both start on Day 1 (See flow diagram below for dosing schedule).

Phase 2 Melanoma Dose Expansion Cohorts (CLOSED)

Cohort	Anti-PD-1/L1 Experience	SD-101 Dose	n	Dosing Schema ^a
1	Naïve	8.0 mg in a single injectable lesion if 1 lesion is selected (Lesion A) or 2.0 mg per lesion if 2 to 4 lesions are selected for injection (Lesion A, Lesion B, Lesion C, Lesion D)	Approximately 60	B
2	Experienced ^b	8.0 mg in a single injectable lesion (Lesion A)	Approximately 25	A
5	Naïve	2.0 mg per lesion in 1 to 4 injectable lesions (Lesion A, Lesion B, Lesion C, Lesion D)	Approximately 25	A1
8	Refractory or resistant ^c	2.0 mg in 1 ml per injection in 1 to 4 separate lesions for lesions measuring up to 5 cm in the longest diameter; or for lesions larger than 5 cm, 2.0 mg in 1 ml per injection in 1 to 4 separate regions where the injections are ≥ 5 cm apart (maximum total dose is 8.0 mg)	Approximately 50	A1

Anti-PD-1/L1 = anti-programmed death receptor-1/ligand 1.

^a Dosing Schema:

A: SD-101 and pembrolizumab dosing both start on Day 1 and patients receive 2 courses of SD-101 (each course, separated by 9 weeks, is 4 weekly doses and then every 3 weeks on schedule with pembrolizumab for 7 additional doses)

B: SD-101 dosing starts on Day 22 at the second dose of pembrolizumab and patients receive 2 courses of SD-101 (each course, separated by 9 weeks, is 4 weekly doses and then every 3 weeks on schedule with pembrolizumab for 7 additional doses)

A1: SD-101 and pembrolizumab dosing both start on Day 1 and patients receive 1 course of SD-101 (4 weekly then every 3 weeks on schedule with pembrolizumab up to Week 51)

^b Received prior treatment regimen containing an anti-PD-1/L1 drug.

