2.6 Clinical Experience With SD-101

In the phase 1, single-blind, dose-escalation trial of systemic SD-101 in 20 healthy normal male volunteers, aged 18 years and over (DV3-HNV-01), adverse events (AEs) included flu-like symptoms such as headache, chills, fatigue, and pyrexia, as well as injection-site reactions such as erythema, induration and pain. Dose-limiting toxicities (DLTs) of severe headache, injection-site induration, and neck pain were observed in 1 subject given 5.0 mg of SD-101, resulting in a halt in Dose Escalation and accrual. Transient lymphopenia was the most common laboratory abnormality observed. There was no evidence of complement activation, coagulation abnormalities, or auto-antibody development.

In the phase 1 single-blind, dose-escalation trial of systemic SD-101 in 28 men and women, aged 18 to 55 years, with chronic hepatitis C virus (HCV) infection, SD-101 was administered alone or in combination with ribavirin (DV3-HCV-01). Including doses up to 5.0 mg of SD-101, the majority of AEs were injection-site reactions (erythema, swelling, pain, and pruritus), influenza-like illness, pyrexia, and myalgia. Most AEs were mild or moderate in reported severity. One subject in the 0.1 mg SD-101/ribavirin group experienced a serious adverse event (SAE) of hyperthyroidism that the investigator considered probably related to SD-101 and unrelated to ribavirin. No deaths occurred during the trial.

A phase 1/2 trial of SD-101 in combination with low-dose radiation therapy for untreated low-grade B-cell lymphoma is completed (DV3-LYM-01). A total of 13 patients were dosed in Phase 1 Dose Escalation (4 cohorts comprising 3 patients at each of SD-101 intratumoral doses of 1.0 mg, 2.0 mg, and 4.0 mg, and 4 patients at the 8.0 mg dose). A total of 16 patients were dosed in Dose Expansion (2 cohorts comprising of 7 patients at the 1.0 mg and 9 patients at the 8.0 mg dose levels). SD-101 was well tolerated. Treatment emergent adverse events consisted mainly of Grade 1 to 2 flu like symptoms or local site reactions, with a trend toward more frequent Grade 3 events at the highest tested dose of 8 mg. Intratumoral SD-101 in combination with low-dose radiation resulted in regression of both treated and untreated sites of disease (systemic or abscopal responses) in subjects with previously untreated indolent B-cell lymphoma.

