12.1 General

This trial is designed to allow preliminary assessments of safety, biological activity, and biomarkers. No pre-specified hypothesis testing will be performed. All analyses of demographics, safety, biological activity, and biomarkers will be descriptive.

Injection-site reactions, AEs, SAEs, and abnormal laboratory values will be summarized by the proportion of patients who experience them.

ORR will be presented as the proportion of patients who achieved CR or PR. The DCR will be presented as the proportion of patients who achieved CR, PR, or stable disease.

In general, categorical data will be summarized as counts and percentages (or proportions) and continuous data will be summarized with descriptive statistics such as mean, standard deviation, median, minimum and maximum.

Final analyses will be carried out after the last participant has completed their last trial visit, the trial database has been authorized by Dynavax as complete and final, and major protocol deviations have been identified. Patient data will be reviewed for major protocol deviations by the Medical Monitor prior to database lock. A listing of patients with major protocol deviations will be provided, sorted by treatment and describing their deviations. Efficacy and safety data from each cohort may be analyzed and reported separately from other cohorts. In addition, safety data will be summarized overall and for each separate tumor indication.

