9.0 STATISTICAL METHODS

This trial is designed to allow preliminary assessments of safety, biological activity, and biomarkers. No pre-specified hypothesis testing will be performed. All analyses of demographics, safety, biological activity, and biomarkers will be descriptive.

Efficacy and safety data will be analyzed and reported separately by Phase 1 dose group or Phase 2 analysis group.

Descriptive statistics, including the number of patients (n), mean, standard deviation (SD), median, minimum, and maximum, will be used to summarize continuous variables. Categorical variables will be summarized by number (n) and percentage (or proportions) of patients in each category. All data processing, summarization, and analyses will be performed using SAS Version 9.3 or higher. Specifications for tables, graphs, and data listings will be provided in the tables, figures, listings (TFL) specifications document.

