9.7 Safety Analyses

Injection related reactions, AEs, SAEs, and abnormal laboratory values will be summarized by the proportion of patients who experience them.

All patients in the safety population will be used in the safety analyses. Safety analyses will be summarized by dose or analysis group.

The treatment-emergent period is defined in [Section 7.1](#).

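### SAP 9.7.4 groups the hematology change tables by tumor type and study-day visit, against the SAP's own dose/analysis-group rule, which pools SD-101 doses and mixes SD-101 exposure within a visit

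*SAP*

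**What the plan says.** SAP 9.7.4 sets the grouping for the hematology tables: "Laboratory test results for neutrophils, lymphocytes, and platelets and their change from baseline will be summarized by tumor type and scheduled visit". It names no dose or analysis group, and it adds: "Laboratory data listings will not be produced as clinically significant abnormal laboratory findings are included in AE data".

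The general rule points elsewhere. SAP 9.7 says "Safety analyses will be summarized by dose or analysis group", and SAP 9.0 says "Efficacy and safety data will be analyzed and reported separately by Phase 1 dose group or Phase 2 analysis group". SAP 9.11 lists the groups for tables and figures: four doses for Phase 1, and for Phase 2 the 2 mg and 8 mg columns within each combination of tumor and prior anti-PD-1/L1 experience.

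The protocol does provide for a summary by tumor, but as an extra. Protocol 12.1 first says that each cohort may be analyzed and reported separately, and then: "In addition, safety data will be summarized overall and for each separate tumor indication".

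The cohorts do not start SD-101 on the same study day. The Protocol Synopsis says: "In melanoma Dose Expansion Cohort 1, SD-101 dosing starts on Day 22 at the second dose of pembrolizumab". HNSCC Cohort 3 follows the same lead-in schedule. All other cohorts, and all of Phase 1, start SD-101 on Day 1.

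**The concern.** Two features of the 9.7.4 tables blur what a reader would want from them.

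The first is dose. A specific instruction normally overrides a general one, so a programmer following 9.7.4 would combine 2 mg and 8 mg within each tumor type, and in melanoma also 1 mg and 4 mg if Phase 1 is included. Dose is a central question in this trial: Protocol 2.8 explains the move from 8 mg to 2 mg per lesion.

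The second is time. Visits are counted from the first dose of study drug. In Cohorts 1 and 3 that is pembrolizumab, if study drug means either agent, as Protocol 6.0 suggests. One visit row can therefore hold patients with different numbers of injections and different times since the last one.

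The counts matter for this drug. In the healthy-volunteer trial described in Protocol 2.6, "Transient lymphopenia was the most common laboratory abnormality observed". Under Protocol 7.1, the neutrophil count decides whether SD-101 may be given. With no laboratory listings, a reader of the report could not separate the doses or exposure states afterwards.

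**Working it through.** **Inputs.** Cohort sizes are from SAP 2.0. Dosing days are from Protocol 4.1 and 7.2 and Appendices 1 to 4. Samples are taken as pre-dose, which Protocol 10.3.6 prefers. Phase 1 is taken at its maximum of 24.

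**Reproducing the plan's figures.** Melanoma: 60 + 25 + 25 + 50 = 160. HNSCC: 4 × 25 = 100. Both agree with SAP 2.0. Schedules generated from the dosing rules give 22 injections ending on Day 421 (Cohorts 1/3), 22 ending on Day 400 (Cohorts 2/4) and 20 ending on Day 358 (Cohorts 5-8), as in Protocol 7.1 and 7.2.

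**Exposure at shared visits.** Each cell gives prior SD-101 injections, then days since the last one.

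| Study day | Cohorts 1/3 | Cohorts 2/4 | Cohorts 5-8 |
|---|---|---|---|
| 22 | 0, none | 3, 7 | 3, 7 |
| 43 | 3, 7 | 4, 21 | 4, 21 |
| 64 | 4, 21 | 5, 21 | 5, 21 |
| 211 | 11, 21 | 11, 42 | 12, 21 |
| 253 | 11, 63 | 14, 7 | 14, 21 |

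Phase 1 matches Cohorts 2/4 through Day 211.

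**Share not yet on SD-101 at Day 22 (f).**
- Melanoma, Phase 2 only: 60/160 = 37.5%.
- Melanoma with Phase 1: 60/(160 + 24) = 60/184 = 32.6%.
- HNSCC: 25/100 = 25%.

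**Effect on the Day 22 mean change.** Let L be the lead-in patients' change as a fraction of the exposed patients' change. Then pooled change / exposed change = (1 − f) + f × L.

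| Table | L = 0 | L = 0.5 |
|---|---|---|
| Melanoma, Phase 2 only | 0.625 | 0.8125 |
| Melanoma with Phase 1 | 0.674 | 0.837 |
| HNSCC | 0.75 | 0.875 |

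The values of L are assumptions. The documents give no lymphocyte data from which to estimate it.

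**Would regrouping alone be enough?** No. SAP 2.0 builds MEL/NAIVE from Cohort 1 (Day 22 start) with Cohort 5 and Phase 1 (Day 1 start), and HNSCC/NAIVE from Cohorts 3 and 6. Before the split into dose columns, the Phase 2 lead-in share is 60/(60 + 25) = 70.6% in MEL/NAIVE and 25/(25 + 25) = 50% in HNSCC/NAIVE. The documents do not say how many Cohort 1 patients fall in each dose column.

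**The case against.** The strongest reply is that these tables are not the only laboratory safety output. SAP 9.7 also plans this: "Injection related reactions, AEs, SAEs, and abnormal laboratory values will be summarized by the proportion of patients who experience them". That sentence sits under the dose/analysis-group rule. SAP 9.7.3 adds TEAEs by preferred term and severity, with listings of all TEAEs. A reader might infer from 9.7.4 that no output will show lymphopenia by dose. The documents do not support that, because clinically significant lymphopenia or neutropenia would appear by group through these routes. They are partial, however. No threshold for an abnormal value is given, the TEAE tables hold only what was judged clinically significant, and neither is indexed to time since SD-101.

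The tumor-type table also has a basis in Protocol 12.1 and could be read as that additional summary. This is fair, but 9.7.4 does not say so and specifies no companion table by dose or analysis group.

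A reader might also infer that pooling pulls the SD-101 effect toward zero at every shared visit. It need not. At Day 43 the lead-in cohorts are closer to their last injection than the others, and at Day 64 all Phase 2 cohorts are 21 days out. Nor does Day 211 set Cohorts 1-4 against Cohorts 5-8: Cohorts 1/3 were last injected on Day 190, as were Cohorts 5-8, so only Cohorts 2/4 differ among the Phase 2 cohorts.

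Three limits on the evidence also stand. The lymphopenia is called transient and comes from one trial of systemic SD-101 in 20 healthy men. Protocol 2.6 does not list it among the most common treatment-related events with the combination. Finally, current Appendices 2 to 4 no longer show Phase 2 hematology at each visit, so the Day 22 sample is inferred from the day-of-dosing neutrophil rule in Protocol 7.1, the Day 22 laboratory example in 7.6 and the SAP's basis in Amendment 8.

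Counting visits from the start of combination treatment is otherwise a legitimate descriptive choice.

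**Conclusion.** The point holds as a conflict within the SAP and a limit on what the hematology change tables can show. As written, SAP 9.7.4 departs from 9.0, 9.7 and 9.11, pools SD-101 doses within tumor type, and places patients with no SD-101 and patients with three injections in the same Day 22 row, with no laboratory listing to separate them.

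The Day 22 mean could understate the change in exposed patients. The factor is 0.63-0.67 in melanoma and 0.75 in HNSCC if the lead-in has no effect, or 0.81-0.84 and 0.875 if the lead-in change is half as large. These figures rest on planned cohort sizes, complete pre-dose Day 22 samples and a fall that persists 7 days after an injection. The true size is unknown, and any loss from mixing doses is not quantified.

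The documents do not establish that the drug's lymphopenia will be hidden, or that every visit is biased in one direction.

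**What to change.** In SAP 9.7.4:

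1. Present neutrophils, lymphocytes and platelets and their change by dose group (Phase 1) and analysis group (Phase 2), as SAP 9.7 already requires.
2. Keep the tumor-type table, and label it as the additional summary under Protocol 12.1.
3. Either show Cohorts 1 and 3 separately at each visit, or add a table indexed to the first SD-101 injection (study Day 22 in Cohorts 1 and 3, Day 1 elsewhere), with the last value before that injection as the reference.

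All of this uses data already collected. The cost is SAP wording and a few more table pages. The re-indexed table would align patients with different prior pembrolizumab exposure, and a footnote should say so.
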